#### **4.2.6 Event-Free Survival**

Event-free survival is a composite endpoint of acute GVHD progression, chronic GVHD, malignancy relapse, and mortality.

#### **Malignancy relapse is defined as follows:**

Relapse is defined by either morphological or cytogenetic evidence of acute leukemia or MDS consistent with pre-transplant features, or radiologic evidence of lymphoma, documented or not by biopsy. Progression of disease applies to participants with lymphoproliferative diseases (lymphoma or chronic lymphocytic leukemia) not in remission prior to transplantation. The event is defined as increase in size of prior sites of disease or evidence of new sites of disease, documented or not by biopsy.

#### **Acute leukemia and MDS – Relapse will be diagnosed when there is:**

- Reappearance of leukemia blast cells in the peripheral blood; or,
- >5% blasts in the bone marrow, not attributable to another cause (e.g. bone marrow regeneration).
- The appearance of previous or new dysplastic changes (MDS specific) within the bone marrow with or without falling donor chimerism; or
- The development of extramedullary leukemia or leukemic cells in the cerebral spinal fluid; or
- The reappearance of cytogenetic abnormalities present prior to transplantation.

#### **Lymphoproliferative Diseases – Relapse or progression will be diagnosed when there is:**

- Appearance of any new lesion more than 1.5 cm in any axis during or at the end of therapy, even if other lesions are decreasing in size. Increased FDG uptake in a previously unaffected site will only be considered relapsed or progressive disease after confirmation with other modalities. In participants with no prior history of pulmonary lymphoma, new lung nodules identified by CT are mostly benign. Thus, a therapeutic decision should not be made solely based on the PET without histologic confirmation.
- At least a 50% increase from nadir in the sum of the product diameters of any previously involved nodes, or in a single involved node, or the size of other lesions (e.g., splenic or hepatic nodules). To be considered progressive disease, a lymph node with a diameter of the short axis of less than 1.0 cm must increase by 50% and to a size of 1.5 x 1.5 cm or more than 1.5 cm in the long axis.

Lesions should be PET positive if observed in a typical FDG-avid lymphoma or the lesion was PET positive before therapy unless the lesion is too small to be detected with current PET systems (<1.5 cm in its long axis by CT).

- In addition to the criteria above, participants with CLL who present in complete remission prior to transplantation may fulfill the relapse definition if there is reappearance of circulating malignant cells that are phenotypically characteristic of CLL.

**\* Institution of any therapy to treat persistent, progressive or relapsed malignancy, including the withdrawal of immunosuppressive therapy or donor lymphocyte infusion, will be considered evidence of relapse/progression regardless of whether the criteria described above were met.**

Event-free survival within each treatment group will be described using the Kaplan-Meier estimator, with event time being the earliest time a patient met one of the various criteria for failure. Participants not meeting a failure criterion will be censored at time of last follow-up. Estimates and confidence intervals will be calculated at 6 and 12 months post-randomization.

#### **4.2.7 Overall Survival (OS)**

Death from any cause will be considered an event for this endpoint. A participant's event time will be censored if lost to follow up. OS at 6 and 12 months will be described using the Kaplan-Meier estimator and 95% confidence intervals will be computed.

#### **4.2.8 Disease-free Survival (DFS)**

Disease-free survival is a composite endpoint of the events death and relapse of the underlying malignancy. A participant's event time will be censored if lost to follow up. DFS at 6 and 12 months will be described using the Kaplan-Meier estimator and 95% confidence intervals will be computed.

#### **4.2.9 GVHD-free Survival**

GVHD-free survival is a composite endpoint of the events death, acute GVHD, and chronic GVHD. The proportion of participants alive and GVHD free at 6 and 12 months

post-randomization will be estimated and compared between treatment groups using the Z test for comparing binomial proportions (or Barnard's Exact Unconditional Test as appropriate).

#### **4.2.10 Non-relapse Mortality (NRM)**

Non-relapse mortality (NRM) consists of deaths due to any cause other than relapse of the underlying malignancy. The cumulative incidence of non-relapse mortality will be estimated for each treatment group using the Aalen-Johansen estimator and groups will be compared using Gray's test, treating relapse as a competing risk. Estimates and confidence intervals will be provided at 6 and 12 months post-randomization.

### **4.3 Analysis of the Exploratory Endpoints**

Since this is a phase II trial with many secondary and exploratory endpoints, no explicit control for multiplicity will be incorporated; rather a significance level of 5% will be used for all comparisons on these outcomes.

#### **4.3.1 Steroid Dose**

Doses of methylprednisolone will be converted to prednisone equivalents by multiplying the methylprednisolone dose by 1.25, while doses of prednisolone are considered equivalent to prednisone. The prednisone dose for each patient at Days 7, 14, 21, 28, 35, 42, 49, and 56 will be recorded. Prednisone doses for each patient will be converted to mg/kg. For participants that weigh over 100kg, maximal starting dose of prednisone will be 200mg (or 2mg/kg based on a modified starting weight of 100kg). For calculation of subsequent prednisone doses/kg on subsequent measures, the modified starting weight of 100kg will be used. The cumulative prednisone dose for each patient at Day 56 will be calculated by adding the doses (end of each week's dose) for each of the first eight weeks of treatment, divided by the number of days of survival during this interval. This mean steroid dose will be described for each treatment group by median and range and will be compared between groups using the Wilcoxon Rank Sum test.

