#### **2.3.3.** Exploratory Objectives are to assess the following:

- 1. Steroid-dose (measured in prednisone-equivalent) on Days 7, 14, 21, 28, 35, 42 and 56.
- 2. Use of topical (skin, GI) agents for acute GVHD therapy.
- 3. Incidence of discontinuation of immune suppression, and immune suppression discontinuation without GVHD or disease progression/recurrence by Days 56, 180, and 365 post-therapy.
- 4. Incidence of EBV-associated lymphoproliferative disorder or EBV reactivation requiring therapy
- 5. Incidence of corticosteroid- and sirolimus-associated complications (collected in all patients):
  - a. Incidence of hyperglycemia (defined as a random glucose >200mg/dL or fasting glucose >126mg/dL) and use of diabetes therapy (use of insulin and/or oral medications to control and/or maintain glucose levels) at baseline, Day 28 and Day 56.
  - b. Change from baseline in functional myopathy score at Day 56 and 6-months post-randomization.
    - i. Hip Flexor and Quadriceps Strength via handheld dynamometer
    - ii. Two Minute Walk Test
    - iii. 5-time Sit-to-Stand
    - iv. Adult Myopathy Assessment Tool (AMAT)
  - c. Incidence of hyperlipidemia as measured by fasting lipid panel at baseline, Days 28, 56 and 180 post-randomization.
  - d. Incidence of post-transplant thrombotic microangiopathy (TMA) by 6 months post-randomization.
- 6. Proportion of patients requiring therapy for CMV-reactivation by day 56 post-randomization.
- 7. Change in patient-reported outcomes from enrollment to Day 56, 6 months and 12 months.
  - a. MD Anderson Symptom Inventory (MDASI)
  - b. FACT-BMT
  - c. MOS Short Form 36 (SF-36)
  - d. PedsQL (Pediatric patients)
- 8. A secondary descriptive analysis will evaluate outcomes for AA3 patients.

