# Table 4.3FOLLOW-UP SCHEDULE

Target day range =  $\pm 3$  days for Day 7 (subsequent visits through Day 56 must be scheduled weekly and within  $\pm 3$  days of target date). Target day range  $\pm 14$  days for Day 90 and 6 months; and  $\pm 28$  days for 12 months.

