#### 1. Steroid Dose

Cumulative steroid dose will be described and compared between the treatment groups using a Wilcoxon Rank Sum test.

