##### **1.1.3 Exploratory Objectives**

The exploratory objectives of the study are to assess:

- Cumulative steroid dose (prednisone-equivalent) through Day 56 post randomization.

- Use of topical (skin, GI) agents for acute GVHD therapy at baseline and during the study's duration.
- Incidence of discontinuation of immune suppression, and immune suppression discontinuation without GVHD or disease progression/recurrence by Days 56, 180, and 365 post-therapy.
- Incidence of EBV-associated lymphoproliferative disorder or EBV reactivation requiring therapy
- Incidence of corticosteroid- and sirolimus-associated complications (collected in all participants):
- Incidence of hyperglycemia (defined as a random glucose >200mg/dL or fasting glucose >126mg/dL) and use of diabetes therapy (use of insulin and/or oral medications to control and/or maintain glucose levels) at baseline, Day 28 and Day 56.
- Hip Flexor and Quadriceps Strength score via handheld dynamometer at baseline, Day 56, and 6 months post-randomization
- Two Minute Walk Test score at baseline, Day 56, and 6 months post-randomization
- 5-time Sit-to-Stand Test score at baseline, Day 56, and 6 months post-randomization
- Adult Myopathy Assessment Tool (AMAT) score at baseline, Day 56, and 6 months post-randomization
- Incidence of hyperlipidemia as measured by fasting lipid panel at baseline, Days 28, 56 and 180 post-randomization.
- Incidence of post-transplant thrombotic microangiopathy (TMA) by 6 months post-randomization.
- Proportion of participants requiring therapy for CMV-reactivation by day 56 post-randomization.
- Change in patient-reported outcomes from enrollment to Day 56, 6 months and 12 months.
- MD Anderson Symptom Inventory (MDASI) score at baseline, Day 56, 6 months, and 12 months post-randomization
- FACT-BMT score at baseline, Day 56, 6 months, and 12 months post-randomization
- MOS Short Form 36 (SF-36) score at baseline, Day 56, 6 months, and 12 months post-randomization
- PedsQL (Pediatric participants) score at baseline, Day 56, 6 months, and 12 months post-randomization
- A secondary descriptive analysis will evaluate all study outcomes in AA3 participants.

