**Exhibit 1501-14: Steroid Dose**

The cumulative prednisone-equivalent dose of steroids through Day 56 is described here. Doses of methylprednisolone will be converted to prednisone equivalents by multiplying the methylprednisolone dose by 1.25, while doses of prednisolone are considered equivalent to prednisone. Prednisone doses for each patient will be converted to mg/kg. For participants that weigh over 100kg, maximal starting dose of prednisone will be 200mg (or 2mg/kg based on a modified starting weight of 100kg). For calculation of subsequent prednisone doses/kg on subsequent measures, the modified starting weight of 100kg will be used. Cumulative prednisone dose for each patient at Day 56 is calculated by adding the doses (end of each week's dose) for each of the first eight weeks of treatment, divided by the number of days of survival during this interval.

Cumulative Steroid Dose at Day 56 by Treatment Group			
	Sirolimus (N=)	Prednisone (N=)	P-value*
Median (range)	XX.X (XX.X, XX.X)	XX.X (XX.X, XX.X)	X.XXX

\* *Wilcoxon Rank Sum test*

*Clarify the population for the endpoint (n=?). If n is not the same as the primary endpoint, explain why (e.g. patient not evaluable, missing data, etc.) Give details of not evaluable if the definition is not pre-specified in the protocol.*

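### The Day 56 steroid-dose formula omits the 7 days that each weekly reading represents, so as written it yields neither the cumulative nor the mean dose it is called

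*SAP*

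**What the plan says.** SAP 4.3.1 fixes the readings: "The prednisone dose for each patient at Days 7, 14, 21, 28, 35, 42, 49, and 56 will be recorded". Each is converted to prednisone-equivalent mg/kg. The end-of-week doses are then added "for each of the first eight weeks of treatment, divided by the number of days of survival during this interval". Protocol 3.3.1 and Exhibit 1501-14 give the same calculation.

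The result has two names. SAP 4.3.1 introduces it as a cumulative dose and then writes "This mean steroid dose will be described for each treatment group by median and range". Elsewhere it is only cumulative:
- Protocol 5.2.6: "Cumulative steroid dose will be described and compared between the treatment groups"
- SAP 1.1.3: "Cumulative steroid dose (prednisone-equivalent) through Day 56 post randomization"
- Exhibit 1501-14: "Cumulative prednisone dose for each patient at Day 56 is calculated by adding the doses"

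The arms are compared with a Wilcoxon rank-sum test. The exhibit's table asks for a median and range and prints no unit.

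A clerical side note: the Protocol objective (synopsis and 2.3.3) reads "Steroid-dose (measured in prednisone-equivalent) on Days 7, 14, 21, 28, 35, 42 and 56", which omits Day 49. Protocol 3.3.1 and SAP 4.3.1 include it.

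**The concern.** A sum of daily doses divided by days is a mean only if every day contributes a dose. Here up to eight days contribute to the numerator and up to 56 to the denominator. A cumulative dose should not be divided by days at all. So the rule, followed literally, yields a number that matches neither of its names.

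Reducing steroid burden is part of the trial's rationale (Protocol 5.1), and this is the planned summary of steroid exposure over the whole first 56 days. A reader who took the exhibit's median as mg/kg/day would understate exposure sevenfold in survivors. The plan also does not say what the sum contains when a patient dies partway through a week or misses a reading, so two programmers could produce different values and different ranks.

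**Working it through.** The plan states no numerical value for this endpoint, so there is no figure to reproduce. The formula can be evaluated directly.

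**Inputs.** Eight readings, Days 7 to 56 (SAP 4.3.1). Prednisone is prescribed in mg/kg/day (Protocol 2.5.4), so a reading on a given day is naturally a single-day dose. The divisor is days alive, at most 56. Constant doses below are illustrations.

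**1. Scale for a Day 56 survivor.** Let S be the sum of the eight readings.
- Formula as written: S/56.
- Average recorded daily dose: S/8 = 7S/56, which is 7 times larger.
- Cumulative dose, each reading standing for 7 days: 7S.

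At a constant 1 mg/kg/day, S = 8. The formula gives 8/56 = 0.143; the mean is 8/8 = 1.0 mg/kg/day; the cumulative dose is 7 × 8 = 56 mg/kg. The written value is 1/7 of the mean and 1/392 of the cumulative dose.

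**2. The alternative reading.** If each week's entry were a weekly total, it would be 7 mg/kg and the result (8 × 7)/56 = 1.0 mg/kg/day. That is a correct mean, but it is not the 56 mg/kg that the word cumulative describes.

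**3. Ranks of survivors with complete records.** All are divided by the same extra factor of 7, so their order is unchanged. A simulated comparison of 60 against 60 gave p = 0.0045 both before and after dividing every value by 7.

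**4. Deaths between visits.** Assume that only completed weeks are summed (the plan does not say) and a constant 2 mg/kg/day:

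| Last day alive | Formula | Value |
|---|---|---|
| 6 | 0/6 | 0 |
| 13 | 2/13 | 0.154 |
| 20 | 4/20 | 0.200 |
| 27 | 6/27 | 0.222 |
| 55 | 14/55 | 0.255 |
| 56 (survivor) | 16/56 | 0.286 |

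All six patients had the same daily dose. Multiplying by 7 alone does not repair this: the Day 13 death becomes 7 × 2/13 = 1.08, not 2.0.

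**5. A missed reading.** Assume it enters the sum as zero (again, the plan does not say). A survivor on 1 mg/kg/day with one missed reading scores 7/56 = 0.125. That ranks below a survivor with complete records on 0.9 mg/kg/day, who scores 7.2/56 = 0.129.

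**6. Check of day weighting.** For the Day 13 death, let the Day 7 reading cover 7 days and the same dose cover the remaining 6: 2 × 7 + 2 × 6 = 26 mg/kg, and 26/13 = 2.0 mg/kg/day, as it should be. With a constant dose this tests the scale and the partial-week rule only.

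**The case against.** The best defence is that this is loose wording. Dividing by days alive and then calling the result a mean suggests that a mean daily dose was intended, and reading the entries as weekly totals gives exactly that. The sentence listing eight recording days points to single-day doses but does not exclude the other reading. This stands in part: the intention may well be sound. The written rule still needs correcting, because on one reading the value is wrong and on both the cumulative label is wrong.

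A second defence is that the plan is not silent on missing data. SAP 2.2 excludes missing values that cannot be adjudicated, and Exhibit 1501-14 asks for an explanation when the number analysed differs and for details of patients who are not evaluable. That also stands, though SAP 2.2 is written mainly about the primary endpoint. Neither text says how the sum treats a partial week or one missed reading out of eight. Steps 4 and 5 are therefore conditional on their stated assumptions.

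Three stronger readings are tempting and not supported.
- That the exhibit's unit is wrong: it prints none. The values would agree with the formula above the table; the fault is the scale, the label and the absent unit.
- That the comparison between arms is invalid: survivors with complete records keep their ranks, and no effect on the difference between arms has been computed.
- That the seven-day weight would free the ranks from the visit schedule: Protocol Table 4.3 says "subsequent visits through Day 56 must be scheduled weekly and within" 3 days of target, and the dose recorded still depends on when the visit falls during a taper. Sampling once a week is a separate limitation that this correction does not remove.

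**Conclusion.** Wrong as written, and minor. On the single-day reading, the reported median and range are on the wrong scale, sevenfold too low for a Day 56 survivor if taken as a mean daily dose. On the weekly-total reading, only the cumulative label is wrong. The two names for one quantity are inconsistent on either reading.

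The consequences are limited. SAP 4.3 and Protocol 3.3 treat the endpoint as exploratory (SAP 1.5 does list it among secondary endpoints), and neither the primary endpoint nor the key secondary Day 28 steroid endpoint (SAP 4.2.1) uses this formula. Rank distortion is confined to patients who die before Day 56 or miss a reading, and depends on how the sum is programmed. For scale, the planning figures of 10% to 13.1% Day 56 mortality (Protocol 5.2.2.2) imply about 60 × 0.10 = 6 to 60 × 0.131 = 8 deaths per arm.

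**What to change.** 1. State that each recorded value is a single-day dose in mg/kg/day.
2. Define cumulative dose (mg/kg) as the sum of each recorded dose times the days it covers, up to Day 56 or death. Weight the partial last week by days alive, and say which recorded dose applies to it.
3. Define mean daily dose (mg/kg/day) as that sum divided by days alive.
4. Name which quantity the rank-sum test uses, and label it with its unit.
5. State one rule for a missed reading and one for a death before Day 7. The rules should keep randomized patients in the analysis where dose records allow, in line with the intent-to-treat population in SAP 2.8.1. Report by arm the number not evaluable. Filling a missed Day 7 reading from the next visit is not a safe default. With a Day 14 reading of 0.5 mg/kg/day, week 1 would become 7 × 0.5 = 3.5 mg/kg, below the 3 × 2 = 6 mg/kg that Protocol 2.5.4 plans for the first three days of the prednisone arm. Nor should deaths before Day 7 be not evaluable by default, since that removes patients on a post-randomization outcome.
6. Make the same edit in Protocol 3.3.1 and 5.2.6, SAP 1.1.3 and 4.3.1, and Exhibit 1501-14. Align the Protocol objective's day list on Day 49.

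The cost is wording and a few lines of code. Protocol 4.4 already requires the steroid dose weekly through Day 56, so no new data are needed and treatment is unaffected.

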#### **4.3.2 Topical Therapy**

The proportion of participants using either topical skin or topical GI steroids at randomization will be estimated for each treatment group. Among participants entering with no topical therapy usage at baseline, the proportion of participants initiating new topical treatment will be described for each treatment group and compared between groups using the Z test for comparing binomial proportions (or Barnard's Exact Unconditional Test as appropriate).

#### **4.3.3 Discontinuation of Immune Suppression**

The dates of discontinuation of corticosteroids and other systemic immune suppressive medications will be recorded. Cumulative incidence of immune suppression discontinuation will be described using the Aalen-Johansen estimator and curves will be compared using Gray's test, treating death as the competing risk. Estimates and

confidence intervals will be provided at Day 56 and at 6 and 12 months post-randomization. A refined endpoint of complete immune suppression discontinuation together with freedom from any GVHD or malignancy progression/recurrence will also be examined, treating death, GVHD, and malignancy progression/recurrence as competing risks. Its cumulative incidence for each treatment arm will be described using the Aalen-Johansen estimator; curves will be compared using Gray's test, treating death as the competing risk; and estimates and confidence intervals will be provided at Day 56 and at 6 and 12 months post-randomization.

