#### 3.3.3. Discontinuation of Immune Suppression

The dates of discontinuation of corticosteroids and other systemic immune suppressive medications will be recorded. Incidence of discontinuation of immune suppression will be assessed at Days 56, 180, and 365 post-therapy. A composite endpoint of complete immune suppression discontinuation together with freedom from any GVHD or malignancy progression/recurrence will also be examined.

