#### 3. Discontinuation of Immune Suppression

Cumulative incidence of immune suppression discontinuation will be estimated (treating death as a competing risk) and curves will be compared using Gray's test. Estimates and confidence intervals will be provided for Day 56, 6 and 12 months post-randomization.

4. Incidence of EBV-associated lymphoproliferative disorder

The incidence of EBV-associated lymphoproliferative disorder or EBV reactivation therapy will be described using the cumulative incidence function, treating death as the competing risk. Cumulative incidence curves will be compared between treatments using Gray's test.

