**Exhibit 1501-16: Discontinuation of Immune Suppression**

Discontinuation of immune suppression consists of discontinuation of corticosteroids and other systemic immune suppressive medications.

Cumulative Incidence of Discontinuation of Immune Suppression by Treatment Arm

[figure not shown]

\* P-value from Gray's test. Death is treated as the competing risk.

Cumulative Incidence Estimates and 95% Confidence Intervals for Discontinuation of Immune Suppression		
Time post-randomization	Sirolimus	Prednisone
Day 56	XX.X (XX.X, XX.X)	XX.X (XX.X, XX.X)
6 months	XX.X (XX.X, XX.X)	XX.X (XX.X, XX.X)
12 months	XX.X (XX.X, XX.X)	XX.X (XX.X, XX.X)

GVHD- and relapse-free discontinuation of immune suppression is a refined endpoint consisting of complete immune suppression discontinuation together with freedom from any GVHD or malignancy progression/recurrence.

Cumulative Incidence of GVHD- and Relapse-free Discontinuation of Immune Suppression by Treatment Arm

[figure not shown]
\* P-value from Gray's test. Death is treated as the competing risk.

Cumulative Incidence Estimates and 95% Confidence Intervals for GVHD- and Relapse-free Discontinuation of Immune Suppression		
Time post-randomization	Sirolimus	Prednisone
Day 56	XX.X (XX.X, XX.X)	XX.X (XX.X, XX.X)
6 months	XX.X (XX.X, XX.X)	XX.X (XX.X, XX.X)
12 months	XX.X (XX.X, XX.X)	XX.X (XX.X, XX.X)

Clarify the population for the endpoint (n=?). If n is not the same as the primary endpoint, explain why (e.g. patient not evaluable, missing data, etc.)

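### SAP 4.3.3 names two different competing-risk sets for the exploratory GVHD- and relapse-free discontinuation endpoint, and does not say which GVHD event counts

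*SAP*

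**What the plan says.** SAP 4.3.3 covers two endpoints in one paragraph. The simple one is discontinuation of immune suppression, with death as the competing risk. The refined one is described in the exhibit as "complete immune suppression discontinuation together with freedom from any GVHD or malignancy progression/recurrence". Three statements bear on how the refined endpoint is analysed:

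- The sentence that introduces it says it is examined "treating death, GVHD, and malignancy progression/recurrence as competing risks".
- The next sentence says "Its cumulative incidence for each treatment arm will be described using the Aalen-Johansen estimator", and continues: "curves will be compared using Gray's test, treating death as the competing risk; and estimates". The phrase about Gray's test is the one already used for the simple endpoint earlier in the paragraph.
- In the exhibit titled Discontinuation of Immune Suppression, the footnote under the second figure (GVHD- and relapse-free discontinuation) reads "P-value from Gray's test. Death is treated as the competing risk". The same footnote stands under the first figure, for the simple endpoint, where it agrees with the text.

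The protocol does not decide between them. Section 3.3.3 says: "A composite endpoint of complete immune suppression discontinuation together with freedom from any GVHD or malignancy progression/recurrence will also be examined". It names no competing risks. The analysis item in section 5.2.6 deals only with the simple endpoint and death.

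**The concern.** Someone who develops GVHD or relapses is, in the sense of the three-risk sentence, no longer a candidate for clean discontinuation. That is why those events are listed as competing risks. If the test recognises death alone, something else must happen to participants with GVHD or relapse, and the SAP does not say what. Censoring them changes the target: the test then compares clean discontinuation as if GVHD and relapse did not occur, and so sets aside the very events that separate the refined endpoint from the simple one. Two programmers could report different p-values from the same data, and each could point to a sentence in the plan.

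A second gap sits underneath. Every participant has acute GVHD at randomization, and neither document says which GVHD event ends eligibility for this endpoint. It could be persistence of the presenting episode, a flare, a new organ, chronic GVHD, or GVHD present on the day immune suppression stops. If the presenting episode counted, everyone would have the competing event at time zero.

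**Working it through.** **No plan figure to reproduce.** The documents state no rate, power or sample size for this endpoint. The inconsistency is established from the text, and the numbers below only show the mechanism.

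**Text check.** Elsewhere the SAP keeps text and footnote aligned when more than one competing risk applies: for chronic GVHD, section 4.2.4 and its exhibit both name death and relapse. The refined endpoint departs from that pattern.

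**Inputs.** From the documents: 60 participants per arm (SAP 2.1), 12 months of follow-up (SAP 1.2.3), two-sided 0.05 (SAP 2.9). Assumed, with no source in the documents: constant yearly hazards *s* (stopping immune suppression), *g* (GVHD or relapse) and *d* (death).

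**Formulas, 12-month incidence.**

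- Three competing risks: s/(s+g+d) × (1 − exp(−(s+g+d)))
- Death only, with GVHD/relapse censored: s/(s+d) × (1 − exp(−(s+d)))

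**Worked case.** With s = 0.6, g = 0.8, d = 0.2:

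- Three risks: 0.6/1.6 × (1 − exp(−1.6)) = 0.375 × 0.798 = 29.9%
- Death only: 0.6/0.8 × (1 − exp(−0.8)) = 0.75 × 0.551 = 41.3%

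**Arm contrasts (d = 0.2 throughout).**

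| Effect of death only | s, arm 1 / arm 2 | g, arm 1 / arm 2 | Three risks | Death only |
|---|---|---|---|---|
| Difference missed | 0.6 / 0.6 | 0.4 / 1.2 | 34.9% vs 25.9% | 41.3% vs 41.3% |
| Difference created | 0.8 / 0.5 | 1.5 / 0.7 | 29.4% vs 26.9% | 50.6% vs 36.0% |
| Difference reversed | 0.8 / 0.5 | 3.0 / 0.5 | 19.6% vs 29.1% | 50.6% vs 36.0% |

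For the reversed row, three risks give 0.8/4.0 × (1 − exp(−4.0)) = 19.6% and 0.5/1.2 × (1 − exp(−1.2)) = 29.1%. Death only gives 0.8/1.0 × (1 − exp(−1.0)) = 50.6% and 0.5/0.7 × (1 − exp(−0.7)) = 36.0%.

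**Effect on the test.** Gray-type tests were simulated with 60 per arm, 12 months and 1,000 replications, again with d = 0.2:

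| s | g | Three-risk test rejects | Death-only test rejects | Tests disagree at 0.05 |
|---|---|---|---|---|
| 0.5 / 0.5 | 1.5 / 0.5 | 17.8% | 4.7% | 19.1% |
| 1.0 / 1.0 | 2.5 / 0.8 | 45.6% | 5.5% | 46.7% |
| 0.8 / 0.5 | 1.5 / 0.7 | 6.0% | 25.8% | 21.4% |
| 0.5 / 0.5 | 1.0 / 1.0 | 4.4% | 4.8% | 2.4% |

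With identical arms (last row) both tests hold their level. They part when the GVHD/relapse hazard differs by arm. The reversed case was computed for the curves only and was not simulated.

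**The case against.** The strongest reply is that this is a slip of wording that nobody would program. The curves to be compared are the Aalen-Johansen curves of the same sentence, and the sentence before sets their competing risks at three. The death-only phrase was probably carried over from the simple endpoint. SAP section 5 says the exhibit shells are illustrative and may change, so the footnote carries little weight. The endpoint is exploratory, and the hazards above are invented. Constant hazards from randomization also fit poorly with a plan to continue sirolimus to at least Day 56 (Protocol 2.5.3).

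Much of this stands. A reader might infer that the reported p-value will certainly belong to a different quantity from the curve printed beside it. The documents do not support that. A programmer who follows the three-risk sentence throughout gets a matching test. The exhibit's curve may itself be death-only, in which case curve and p-value agree with each other and conflict only with the three-risk sentence. Nor do the documents say that GVHD and relapse would be censored. If those participants simply stay at risk without an event, the result is close to the three-risk analysis.

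The reply does not remove the contradiction. It lies within section 4.3.3 even if the footnote is set aside, and a likely explanation for it is not a rule. The reply also leaves open which GVHD event counts.

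**Conclusion.** The competing-risk set for the refined endpoint is stated inconsistently, and the GVHD event is undefined. Under the literal death-only rule with GVHD/relapse censored, the test no longer addresses the three-risk cumulative incidence. It can then hide a difference (34.9% vs 25.9% becomes 41.3% in both arms), create one, or reverse one. These sizes rest on assumed constant hazards and on censoring, and they are not forecasts for this trial. A reader might also infer that the reported incidence itself will be overstated, as 41.3% against 29.9%. That follows only if the estimate, and not just the test, is coded death-only with censoring.

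The reach is small: one exploratory estimate and its p-value. The primary analysis, sample size and safety monitoring are untouched. A correction is warranted because it is cheap and the coding should be settled before data lock in an open-label trial.

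**What to change.** - In the refined-endpoint sentence of SAP 4.3.3, name death, GVHD and malignancy progression/recurrence as competing events for both the Aalen-Johansen estimate and Gray's test.
- Make the same change in the second footnote of the Discontinuation of Immune Suppression exhibit, under the GVHD- and relapse-free figure. Identify the exhibit by title, since two exhibits carry the number 1501-16.
- Define which post-randomization GVHD event counts as the competing event, and how the episode present at entry is treated. The coding cannot be written without this.
- Keep death as the only competing risk for the simple discontinuation endpoint and its footnote.

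The cost is a few sentences in the SAP and one footnote. There is no evident need for new data, since GVHD status, relapse, death and immune-suppression use are already collected at the scheduled visits.
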